The data from Ellebedy et. al. (18) suggest that it is likely that the H5N1 pISV will induce a stalk-specific response in the control cohort as well as the pLAIIV primed subjects, but we hypothesize that recipients of the H2N2, H6N1 and H9N2 pLAIIVs will have more memory B cells against the group 1 stalk than the control cohort because they differ from the control cohort in having received two doses of a different group 1 virus (H2N2 or H6N1 or H9N2). It is now 9 years since the emergence of the 2009 pandemic H1N1 virus and people would have been exposed to the virus or vaccine more than once so they will have a predominantly head-specific response to H1N1pdm09 as reported by Andrews et. al. (23).

Additionally, Yassine et. al. (24), reported that not all broadly neutralizing antibodies are created equal; using stalk stabilized probes against H1 seasonal, H1 pdm09, H2, H5 and H9 HA stems, they found that ~45% of 202 people had antibodies that bound the stalks of non-circulating viruses (H2, H5, H9) and 30% had antibodies that bound 4 of the 5 probes. They reported that sera collected either prior to the 2009 pandemic or afterwards showed no differences in cross-reactivity and they observed no difference in the profiles of cross-reactive sera from vaccinated and non-vaccinated subjects collected after the H1N1 pandemic emergence. However, there was a statistically significant boost in specific stalk antibody titers to H1 CA 09 HA SS probe in subjects that received pandemic H1N1 influenza vaccine compared to those that did not receive the vaccine within the same time period. They also noted a higher rate of cross-reactive antibodies in the older population, especially those born within or before the period of H2N2 pandemic (24).

We will use similar probes (25) to detect stalk antibodies in the sera from this trial and hypothesize that on administration of an H5N1 inactivated vaccine, we will see a stalk-specific antibody response in both cohorts but the magnitude of the response and the breadth of the stalk antibody response in the pLAIIV primed subjects will be greater than in the controls.

In summary, we hypothesize that people that have been primed with pLAIIVs bearing novel HAs will develop antibodies that react more broadly than people whose only exposure to a novel HA head was H1N1pdm09.

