4.1 Inclusion Criteria

All the following criteria must be met for a subject to be enrolled in this trial:

1. Adult males and non-pregnant females between 18 years and 60 years of age inclusive.
2. General good health, without significant medical illness, physical examination findings, or significant laboratory abnormalities as determined by the investigator.
3. Available for the duration of the trial.

4. Able to demonstrate understanding of key study concepts, study rationale, and study participation requirements by scoring $\geq 70\%$ on a written comprehension assessment in ≤ 3 attempts.
5. Willingness to participate in the study as evidenced by signing the informed consent document.
6. Willingness to allow storage and testing of laboratory samples for future research.
7. Received 2 doses of live attenuated H2N2, H6N1, or H9N2 vaccine in a prior trial (Cohort 1) or H2N2, H6N1 and H9N2 naïve (Cohort 2)
8. Willingness to forego seasonal influenza virus vaccination from 1 month before vaccination until 3 months after vaccination.
9. Female subjects of childbearing potential must agree to have used effective birth control methods beginning at least one month prior to vaccination, and continuing with ‘per label/fully effective use’ for the chosen method for duration of the study, from amongst these:
 - pharmacologic/hormonal contraceptives, including oral, parenteral, subcutaneous, and transcutaneous delivery;
 - condoms with spermicide;
 - diaphragm with spermicide;
 - intrauterine device;
 - absolute abstinence from heterosexual intercourse as a matter of normal preferred lifestyle;

or must be surgically sterile or must be age 50 AND have had no menses at all for at least one full year.

All females must provide urine for pregnancy testing prior to enrollment (immediately prior vaccination), as well as a statement of menstrual history and a summary of all potentially reproductive sexual activity for the month prior to vaccination, and at each study contact throughout the study, and report known or suspected pregnancy immediately.

10. Willingness to refrain from blood donation during the course of the study.

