6.6 Treatments that Could Potentially Interfere with Vaccine-Induced Immunity

The following criteria will be reviewed with the subjects during each follow up visit up to and including day 90. If any of these become applicable during the study, it will be noted in the subject's record. The subject will not be included in further immunogenicity evaluations as of the visit in which the exclusionary treatment was reported. Subjects will be encouraged to participate in the safety evaluations, including blood draws at the discretion of the investigator for the duration of the study.

1. Use of any investigational drug or investigational vaccine other than the study article within 90 days of receipt of the study agent.
2. Administration of chronic (defined as more than 14 days) immunosuppressants or other immune-modifying drugs (topical and nasal steroids are allowed).
3. Receipt of any licensed vaccine in the 4 weeks after vaccination.
4. Receipt of immunoglobulins and/or any blood products.

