6.7 Concomitant Medications

A concomitant medication (con-med) is a drug or biological product, other than a study drug, taken by a subject during a clinical trial. Information about routine medication use will be documented in the screening medical history. Concomitant medications and changes in pre-existing medication regimens indicating new diagnoses or worsening of a pre-existing condition will be collected from vaccination to Day 28 to identify solicited and unsolicited AE's, new or changed significant or chronic conditions and treatments potentially interfering with vaccine immunity. Between day 28 and 90 concomitant medications will only be collected if associated with an SAE or with a treatment that interferes with vaccine-induced immunity as above.

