6.8 Study Procedures By Day

See [Appendix A](#) for a tabular representation of study procedures. In the description below, Study Day 0 is the day of receipt of vaccine. The days are numbered thereafter.

Study Day 0 (Day of Vaccination/Enrollment)

1. Verify that study-specific Informed Consent was obtained.
2. Ensure that all inclusion/exclusion criteria are met.
3. Record vital signs (blood pressure, temperature, heart rate, and respiratory rate).
4. Perform an abbreviated history and focused physical examination.
5. For women, obtain urine for β -HCG testing. Ensure the test is negative before proceeding; a positive test will exclude the subject from the trial.
6. Obtain blood for Serum and for PBMCs.
7. Administer the vaccine.
8. Observe for at least 30 minutes after vaccination to evaluate for immediate adverse reactions.
9. Record vital signs (blood pressure, temperature, heart rate, and respiratory rate) 30 minutes after vaccination.
10. Review pregnancy prevention Counseling (Females only).

Study Day 7 \pm 1 Day

1. Obtain interim history and perform focused physical examination, concentrating on any acute complaints and adverse events after vaccination.
2. Assess continuing eligibility and for treatments that could potentially interfere with vaccine-induced immunity.
3. Record vital signs. (blood pressure, temperature, heart rate).
4. Evaluate injection site.
5. Perform an abbreviated history and focused physical examination.
6. Obtain blood for serum and for PBMCs.
7. Review Pregnancy Prevention counseling (Females only).

Study Day 14 \pm 2 Day

1. Obtain interim history concentrating on any acute complaints.

2. Assess continuing eligibility. Review use of any concurrent medications. Assess for treatments that could potentially interfere with vaccine-induced immunity.
3. Perform focused physical exam if indicated.
4. Record vital signs. (blood pressure, temperature, heart rate).
5. Obtain blood for serum and PBMCs.
6. Review pregnancy prevention counseling (Females only).

Study Day 28 ±7 Days

1. Obtain interim history concentrating on any acute complaints.
2. Assess continuing eligibility. Review use of any concurrent medications. Assess for treatments that could potentially interfere with vaccine-induced immunity.
3. Perform focused physical exam if indicated.
4. If female, obtain urine for β -HCG testing.
5. Obtain blood for serum and PBMCs.

Study Day 56 ±7 Days

1. Perform basic history, concentrating on any acute complaints.

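### Subjects agree to avoid seasonal influenza vaccine for 3 months, but the immunogenicity rule counts a licensed vaccine for only 4 weeks, so Day 56 and Day 90 stalk titres after a Day 29 to 90 vaccination stay in the analysis

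*Combined protocol and SAP*

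**What the plan says.** Section 4.1, inclusion criterion 8, sets this condition of entry: "Willingness to forego seasonal influenza virus vaccination from 1 month before vaccination until 3 months after vaccination".

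Section 6.6 governs which subjects stay in the immunogenicity evaluation. It begins "The following criteria will be reviewed with the subjects during each follow up visit up to and including day 90", and the consequence of meeting a criterion is "The subject will not be included in further immunogenicity evaluations as of the visit in which the exclusionary treatment was reported". Only item 3 of its four criteria reaches a licensed vaccine: "Receipt of any licensed vaccine in the 4 weeks after vaccination". Item 1 has a longer window, but for investigational products only: "Use of any investigational drug or investigational vaccine other than the study article within 90 days of receipt of the study agent". Items 2 and 4 concern chronic immune-modifying drugs, and immunoglobulins or blood products.

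Section 6.7 ties later recording to the same list: "Between day 28 and 90 concomitant medications will only be collected if associated with an SAE" or with an interfering treatment of the kind defined in section 6.6.

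In section 6.8, the lists for Days 7, 14 and 28 each include an explicit check for interfering treatments. The lists for Days 56 and 90 do not; their history item is "Perform basic history, concentrating on any acute complaints". Appendix A shows an interim history at both visits but has no row for the check.

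Section 10 defines no immunogenicity population and no rule for samples taken after another vaccine. Section 10.4 gives the primary endpoint as a fold rise in group 1 stalk antibody and names no sampling day. Longevity of the stalk response is an exploratory objective (sections 2.3 and 10.7).

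**The concern.** The protocol treats seasonal influenza vaccine as something to avoid for 3 months, yet its analysis rule stops reacting to it after 4 weeks. A subject vaccinated on Day 40 has departed from the undertaking given at entry but meets no criterion in section 6.6, so the Day 56 and Day 90 sera are analysed as though only the study vaccine had been given. By contrast, an investigational vaccine on the same day would remove those sera.

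Because section 6.7 records later treatments only if they belong to the section 6.6 list or accompany an SAE, the vaccination may leave no trace in the data. It could not then be reliably handled afterwards.

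The assay target is group 1 stalk antibody, and section 1.4 counts H1N1pdm09 as a group 1 stalk exposure. The cohorts are not randomised and are recruited by different routes (section 6.2), so equal uptake of seasonal vaccine cannot be assumed. An uptake difference would enter the cohort comparison at the later visits, and a late boost could pass for persistence of the response.

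**Working it through.** **Windows.** Sections 2.2 and 10.5 describe the same SAE period as 90 days and as 3 months, so 3 months is read here as Day 90.

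- Period in which seasonal vaccine is to be avoided after dosing: to Day 90.
- Period in which a licensed vaccine triggers exclusion: 4 weeks, to Day 28.
- Uncovered: 90 − 28 = 62 days (Days 29 to 90), or 62/90 = 69% of the period.

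**Samples affected.** Visit windows are from section 6.8.

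| Visit | Allowed days | Can follow a vaccination on Day 29 or later? |
|---|---|---|
| Day 7, Day 14 | 6–8, 12–16 | No |
| Day 28 | 21–35 | Only if held late: at most 35 − 29 = 6 days after it |
| Day 56 | 49–63 | Yes |
| Day 90 | 76–104 | Yes |

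Day 360 lies outside both windows and is not part of this point.

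**Other safeguards.** Withdrawal for noncompliance (section 4.5) needs a consistent pattern that prevents adequate follow-up or threatens safety or data integrity. It is not a rule about individual samples. Nothing in section 10 removes the sera.

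**Size.** The documents give neither the uptake on Days 29 to 90 nor the size of a seasonal boost, so both are assumed. If m of n subjects in a cohort have their titre multiplied by b, the mean log titre rises by (m/n) × log b and the geometric mean is multiplied by b^(m/n). Cohort sizes are from the immunization schedule table.

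| n | 1 subject, b = 1.2 | 1 subject, b = 2 | 3 subjects, b = 1.2 | 3 subjects, b = 2 |
|---|---|---|---|---|
| 12 (Cohort 1) | 1.015 | 1.059 | 1.047 | 1.189 |
| 15 (Cohort 1) | 1.012 | 1.047 | 1.037 | 1.149 |
| 20 (Cohort 2) | 1.009 | 1.035 | 1.028 | 1.110 |

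For example, 1.2^(1/12) = 1.015 and 2^(3/12) = 1.189. These are shifts in one cohort with no vaccination in the other. If both have some, the cohort ratio changes by b^(m1/n1 − m2/n2), so equal proportions cancel.

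**The case against.** The strongest reply is that the contaminating signal should be weak. Section 1.4 says that seasonal vaccine containing the H1N1pdm09 HA boosts stalk memory B cells very little, that the stalk response was not seen on revaccination, and that stalk titres did not rise between 2010 and 2014. The contrary sentence in the same section, "there was a statistically significant boost in specific stalk antibody titers to H1 CA 09 HA SS probe", describes recipients of pandemic H1N1 vaccine, not seasonal vaccine. This stands, and it is why the illustration starts at a 1.2-fold boost.

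Uptake may also be low. Every subject agrees to forego the vaccine, and free seasonal vaccine is offered before enrolment, with a 30-day deferral for those who accept at the study-specific visit (sections 6.2 and 6.3). Criterion 8 is a statement of willingness at entry, so the gap matters only when a subject later departs from it. This also stands.

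The review to Day 90 is already required by section 6.6, and Appendix A schedules a history at both visits. That helps only in part: staff would be reviewing a list on which a Day 40 seasonal vaccine does not appear.

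Finally, excluding samples because of an event after dosing can itself introduce selection in non-randomised cohorts this small. That is fair, and it is why the fix includes a sensitivity analysis.

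**Conclusion.** The mismatch is real and no other section closes it. As written, Day 56 and Day 90 stalk titres taken after an exposure that the protocol itself restricts remain in the analysis, possibly without a record. The effect is probably small: about 1.5% to 19% on the geometric mean of a 12-person cohort, assuming a 1.2- to 2-fold boost in one to three subjects. It bears mainly on the exploratory longevity objective.

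Three stronger readings are not supported:

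- A reader might infer that the primary comparison is seriously biased against its 2.0- to 2.1-fold target (section 10.2). A 4-fold seasonal boost with a 30-point uptake difference would give 4^0.3 = 1.52, but 4-fold is the rise that section 10.2 assumes for the H5N1 study vaccine in naïve subjects, and section 1.4 expects far less from seasonal vaccine. The primary endpoint names no day, so Days 56 and 90 reach it only if chosen. The emphasis on Day 28 in sections 4.6 and 11.6 suggests an earlier day.
- A reader might infer that Day 28 serum is compromised. That needs a late visit and a vaccination on Days 29 to 35, leaving at most 6 days for a response.
- A reader might infer that dropping samples after an unrelated licensed vaccine in the first 4 weeks is an error. Section 6.6 addresses interference with immunity in general, and this is a prespecified choice.

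**What to change.** Reconcile inclusion criterion 8 with sections 6.6 and 6.7:

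1. In the section 6.6 immunogenicity rule, extend the window for influenza vaccines to match criterion 8, through Day 90. Leave the 4-week rule for other licensed vaccines as it is.
2. Exclude samples drawn after such a vaccination from the main immunogenicity analysis, and report a sensitivity analysis that includes them.
3. Add the section 6.6 check, and recording of any influenza vaccine with its date, to Days 56 and 90 in section 6.8 and Appendix A. Make clear in section 6.7 that this recording is required.

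The cost is a sentence or two in sections 6.6 and 6.7 and a line at two visits. A few Day 56 and later samples may be dropped from the main analysis, which matters most in a cohort of 12 to 15; the sensitivity analysis shows whether the loss affects the result. The change concerns which samples are analysed and what is recorded, not the care of subjects.

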6.7 Concomitant Medications

A concomitant medication (con-med) is a drug or biological product, other than a study drug, taken by a subject during a clinical trial. Information about routine medication use will be documented in the screening medical history. Concomitant medications and changes in pre-existing medication regimens indicating new diagnoses or worsening of a pre-existing condition will be collected from vaccination to Day 28 to identify solicited and unsolicited AE's, new or changed significant or chronic conditions and treatments potentially interfering with vaccine immunity. Between day 28 and 90 concomitant medications will only be collected if associated with an SAE or with a treatment that interferes with vaccine-induced immunity as above.

6.8 Study Procedures By Day

See [Appendix A](#) for a tabular representation of study procedures. In the description below, Study Day 0 is the day of receipt of vaccine. The days are numbered thereafter.

Study Day 0 (Day of Vaccination/Enrollment)

1. Verify that study-specific Informed Consent was obtained.
2. Ensure that all inclusion/exclusion criteria are met.
3. Record vital signs (blood pressure, temperature, heart rate, and respiratory rate).
4. Perform an abbreviated history and focused physical examination.
5. For women, obtain urine for β -HCG testing. Ensure the test is negative before proceeding; a positive test will exclude the subject from the trial.
6. Obtain blood for Serum and for PBMCs.
7. Administer the vaccine.
8. Observe for at least 30 minutes after vaccination to evaluate for immediate adverse reactions.
9. Record vital signs (blood pressure, temperature, heart rate, and respiratory rate) 30 minutes after vaccination.
10. Review pregnancy prevention Counseling (Females only).

Study Day 7 \pm 1 Day

1. Obtain interim history and perform focused physical examination, concentrating on any acute complaints and adverse events after vaccination.
2. Assess continuing eligibility and for treatments that could potentially interfere with vaccine-induced immunity.
3. Record vital signs. (blood pressure, temperature, heart rate).
4. Evaluate injection site.
5. Perform an abbreviated history and focused physical examination.
6. Obtain blood for serum and for PBMCs.
7. Review Pregnancy Prevention counseling (Females only).

Study Day 14 \pm 2 Day

1. Obtain interim history concentrating on any acute complaints.

2. Assess continuing eligibility. Review use of any concurrent medications. Assess for treatments that could potentially interfere with vaccine-induced immunity.
3. Perform focused physical exam if indicated.
4. Record vital signs. (blood pressure, temperature, heart rate).
5. Obtain blood for serum and PBMCs.
6. Review pregnancy prevention counseling (Females only).

Study Day 28 ±7 Days

1. Obtain interim history concentrating on any acute complaints.
2. Assess continuing eligibility. Review use of any concurrent medications. Assess for treatments that could potentially interfere with vaccine-induced immunity.
3. Perform focused physical exam if indicated.
4. If female, obtain urine for β -HCG testing.
5. Obtain blood for serum and PBMCs.

Study Day 56 ±7 Days

1. Perform basic history, concentrating on any acute complaints.
2. Obtain blood for serum and PBMC's.

Study Day 90 ±14 Days

1. Perform basic history, concentrating on any acute complaints.
2. Obtain blood for serum and PBMCs.
3. If female, obtain urine for β -HCG testing

Study Day 360 ±30 Days

1. Perform basic history, concentrating on any acute complaints.
2. Obtain blood for serum and PBMCs.

6.9 Clinical and Research Laboratory Testing

For both cohorts, the maximum volume of blood to be drawn is approximately 755 mL over the 12 month study period and not more than 550 ml's in any 8 week period, which should not compromise the health of trial subjects and is consistent with the NIH guidelines set forth in the M95-9 (rev) "Guidelines for Limits of Blood Drawn for Research Purposes in the Clinical Center ."

Using standard techniques, and with samples labeled with a unique study identifier for each subject, Quest Laboratories will perform the following tests:

1. Complete blood count plus white blood cell differential and platelets.
2. Chemistry panel (if indicated).
3. HIV assay (4th generation ELISA with Western blot confirmation).
4. HBsAg ELISA

5. HCV RNA PCR confirmation.
6. Serum pregnancy test (if indicated)

Urine β -HCG testing will be performed at the clinical trial site using an FDA-approved urine pregnancy test kit.

HAI assays done for the purpose of screening potential subjects will be done by the CIR laboratory.

Quantitative ELISA and MN for anti-stalk antibody, the passive serum transfer study, and the LD50 challenge study in mice will be assessed at the Icahn School of Medicine at Mount Sinai.

Assessment of Plasmablasts and Memory B cells responses will be conducted at the Vaccine Research Center, NIH.

De-identified PBMCs may be sent to Adaptive Biotechnology for immune profiling.

Nasal secretions will be obtained by nasal lavage using 20 mL of Lactated Ringer's Solution for Injection (10 mL per nares) with the glottis in a closed position. The collected lavage secretions will be used to screen for adventitious agents should subjects report URI symptoms during the 28 day post-vaccination AE reporting period.

Specimens will be stored at the clinical trial site or the Laboratory of Infectious Diseases (LID), National Institute of Allergy and Infectious Diseases (NIAID). Access to research samples will be limited using a locked room. Samples and data will be stored using codes assigned by the investigators. Laboratory data will be kept in password-protected computers. Only investigators will have access to the samples and data. Samples at the clinical trial site are tracked manually on specimen logs that are kept in a separate, locked file cabinet.

Any loss or unanticipated destruction of samples that compromises the scientific integrity of the data collected for the study (for example, due to freezer malfunction) will be reported to the IRB.

6.10 Testing of previous samples

Samples from the subjects in the previous pLAIV studies are still stored in the NIAID repository. With subject consent, pre-and post pLAIV serum samples will be retrieved and tested for anti-stalk antibodies, in parallel with the samples collected during this study.

